## 2. Study overview

[figure not shown]
The objective of the COG-T CHD study is to determine the efficacy of computerized cognitive training on global cognitive function in patients with CHD and cognitive impairment compared with positive controls, over a 12-week training period. At the same time, we will continue the follow-up until week 24 to determine whether the effects of the intervention are sustained and investigate the changes of head MRI structure and function in the computerized cognitive training group and the positive control group were observed at week 12/24.

### 2.1 Study design

This study was a multicentre, double-blind, parallel randomized controlled study using a 1:1 parallel control design. A total of 200 patients with coronary heart disease combined with cognitive decline but no dementia will be enrolled from 8 centres (Beijing Anzhen Hospital affiliated to Capital Medical University, Peking University Third Hospital, The second hospital of Chifeng, The First Affiliated Hospital of Hebei North University, Handan Central Hospital, The First Hospital of Hebei Medical University, Beijing Sixth Hospital, Inner Mongolia Ordos Central Hospital Kangbashi Department). All patients were stratified and randomly assigned to the cognitive digital therapy group and the positive control group according to age and educational level, and were given cognitive training at least 5 times a

week for at least 30 minutes each time for a total of 12 weeks. All subjects were interviewed at 12 weeks. After completing the 12-week visit, the researchers will unblind the subjects, the positive control group will end the intervention, and the cognitive digital therapy group will repeat the intervention 1:1 randomization: One group ended the cognitive training, and the other group continued the training until 24 weeks. Each patient will be followed up to 24 weeks. The primary outcome was the proportion of improvement in overall cognitive function at 12 weeks, defined as 0.67 standard deviation (SD) above baseline cognitive function as measured by the Basic Cognitive Ability Test (BCAT). (see Fig. 1)

Fig. 1 Participant flow through study

## 2.2 Intervention Description

A total of 200 patients were randomly divided into the following two groups according to age ( $\geq 75$  years old,  $< 75$  years old) and education level (completion of junior high school and below, senior high school and above) :(1) cognitive digital therapy group; (2) Positive control group.

### Cognitive digital therapy group

The patients in the cognitive digital therapy group were trained in multi-dimensional cognitive function, including attention, memory, executive function, thinking, processing speed and perception. The system will adaptively adjust the training difficulty and training plan according to the patient's current training time and training results, and train the patient's weak cognitive ability as much as possible. The patients had the same total amount of training per day.

### **Positive control group**

The training content of the positive control group was cognitive training tasks with weak difficulty or no difficulty change. The patients underwent cognitive function training with a fixed program, including 15 training items, and the internal difficulty of the training items remained constant. The system presents the training content randomly according to the training scheme. The patients had the same total amount of training per day.

### **2.3 Sample size calculation**

The sample size was calculated based on previous studies and the following assumptions (see Fig. 2) :

1. After 12 weeks of intervention, 30% of patients in the cognitive digital therapy group improved their overall cognitive scores (0.67SD);
2. The overall cognitive score of positive control group was improved by 10%;
3. Bilateral test ( $\alpha=0.05$ ) was adopted, the minimum efficacy of the test was 90%, the 3-month loss rate was assumed to be 20%, the sample size was calculated  $N=198$ , and 200 patients were finally included.

Fig. 2: Sample size

#### **Dropout-Inflated Sample Size**

Dropout Rate	Sample Size			Dropout-Inflated Enrollment Sample Size			Expected Number of Dropouts		
	N1	N2	N	N1'	N2'	N'	D1	D2	D
20%	79	79	158	99	99	198	20	20	40

## ***2.4 Aims and objectives***

To determine the effectiveness of the computerized cognitive training on the overall cognitive function in patients with CHD and cognitive impairment without dementia, compared to positive controls, over a 12-week training.

## ***2.5 Outcomes***

### ***2.5.1 Primary outcome***

The primary endpoint of the study will be the proportion of subjects with improved global cognitive function at 12 weeks. As described in section 2.3, the cognitive function will be evaluated by BCAT. The BCAT will include four distinct brain functions, namely processing speed, working memory, episodic memory and visuospatial. The global cognitive function score will be calculated as the average of scores across each cognitive domain. In the DELIGHT trial, clinically significant improvement in cognitive function was defined as a Z-value of the overall BCAT score that was 0.67 SD (2 points of task score) higher than the baseline Z-value after 12 weeks training. The Z-value for each cognitive domain can be obtained by referring to the Z score conversion table (Table.1.2).

Table 1. The correspondence between BCAT cognitive ability scores and Z-scores

BCAT score	Z-score
19	3.00 (2.83 ~ 3.17)
18	2.67 (2.50 ~ 2.83)
17	2.33 (2.17 ~ 2.50)
16	2.00 (1.83 ~ 2.17)
15	1.67 (1.50 ~ 1.83)
14	1.33 (1.17 ~ 1.50)
13	1.00 (0.83 ~ 1.17)
12	0.67 (0.50 ~ 0.83)
11	0.33 (0.17 ~ 0.50)
10	0.00 (-0.17 ~ 0.17)
9	-0.33 (-0.50 ~ -0.17)
8	-0.67 (-0.83 ~ -0.5)
7	-1.00 (-1.17 ~ -0.83)
6	-1.33 (-1.50 ~ -1.17)
5	-1.67 (-1.83 ~ -1.50)
4	-2.00 (-2.17 ~ -1.83)
3	-2.33 (-2.50 ~ -2.17)
2	-2.67 (-2.83 ~ -2.50)
1	-3.00 (-3.17 ~ -2.83)

Table 2. Threshold for basic cognitive impairment in different age groups based on BCAT

	18-29 years old	30-39 years old	40-49 years old	50-59 years old	60-59 years old	Over 70 years old
processing speed	-0.16	-0.43	-0.69	-1.09	-1.39	-1.71
working memory	-0.25	-0.45	-0.74	-1.01	-1.26	-1.43
episodic memory	-0.34	-0.52	-0.80	-1.07	-1.20	-1.47
visual space	-0.53	-0.69	-0.76	-0.90	-1.05	-1.22

### 2.5.2 Secondary outcomes

- 1) The proportion of clinically significant improvement (2 points of task score) in global cognitive function from baseline at 24 weeks;
- 2) The proportion of improvement in cognitive function from baseline in each cognitive domain at 12 weeks and 24 weeks;
- 3) Changes in global cognitive function scores in the intervention group compared to the control group from baseline to week 12 and 24;
- 4) Changes in subjects' self-efficacy scores from baseline to 12 weeks and 24 weeks; Self-Efficacy scores was measured by the Chinese version of the General self-efficacy Scale-Schwarzer (GSES).
- 5) Changes in subjects' quality of life scores from baseline to 12 weeks and 24 weeks; Quality of life scores was measured using the European Five-Dimensional Health Scale (EQ- 5D-3L).
- 6) Changes in subjects' anxiety and depression scores from baseline to 12 weeks and 24

weeks. Anxiety-depression status was measured by the Subject Health Questionnaire: Depression Scale (PHQ-9) and the Generalized Anxiety Scale (GAD-7).

#### *2.5.3 Exploratory outcome*

Changes in structural and functional characteristics of brain MRI will be evaluated at week 12/24 compared to baseline. Consented participants will undergo 3.0T MRI imaging to assess changes in head MRI structure and function before and after cognitive training.

### **3. Population and subgroups to be analyzed**

The full analytical population included all randomized subject who completed the baseline assessment and took at least 1 intervention session, regardless of their adherence to the rest intervention. This analytical population set following the modified intention to treat analysis will be used for primary and secondary efficacy analysis.

### **4. Statistic**

#### *4.1 General analysis considerations*

The analyses will be conducted using SAS 9.4 statistical software. Descriptive statistics will be computed, including the sample size (n), means, standard deviations, medians, and inter and frequency counts and percentages for categorical variables. The efficacy endpoint will be summarized by assessment time points (baseline, 12, 24 weeks) and by intervention groups. Data will be examined for skewness and outliers. Categorical variables are shown as n (%), and continuous variables as mean (standard deviation [SD]) if normally distributed or median (interquartile range [IQR]) if there was a skew distribution. Shapiro-Wilktest will be used to test the normality, the data will be presented as a median (interquartile range) and transformed to approximate a normal distribution. If transformation is not feasible, a

Wilcoxon test can be performed.

The following descriptive data will be present by intervention groups:

Demography characteristics:

Gender(female%), Age(n), Education level (middle school or below, high school or above)

Laboratory measure(n):

BMI, Pulse, Blood pressure (baseline,12 weeks and 24 weeks), Blood test (FBG, TG, etc.),

Electrocardiogram result (sinus rhythm/other), Doppler echocardiography (LVEF, etc.)

Medical/Cardiovascular disease history

Drug usage: Types of drugs and dosages

Self-reported disease/surgical history: Hypertension, Coronary artery disease, Coronary artery bypass/Stenting surgery, neurological disease etc.

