#### *4.4.2 Main secondary efficacy analyses*

The main secondary efficacy analyses will include comparison the intervention group and the control group for the 12-week endpoint analysis and three study groups after the re-randomization at 12 weeks, including the continue training group, stop training group and the control group at the baseline randomization, for the 24 weeks endpoint analysis. All statistical tests of the secondary analyses will be 2-sided, both 95% confidence intervals and p values will be reported.

- 1) The mean value of changes in scores of global cognitive functions from baseline to 12 weeks will be compared using independent t-test between the intervention group and control group. In cases any of domains' score not following normal distribution, if the transformation is not feasible, either the Wilcoxon test or Friedman M test will be used.
- 2) Difference in the proportion of improvement in global cognitive function after 24 weeks will be compared using Pearson chi-square test between continue training group and control group. Adjustment will be performed if necessary.

- 3) The mean value of changes in scores of global cognitive functions from baseline to 24 weeks will be compared using independent t-test between continue training group and control group. Adjustment will be performed if necessary.
  
- 4) The mean value of changes in scores of global cognitive functions from baseline to 24 weeks will be compared using independent t-test between the stop training group and control group. Adjustment will be performed if necessary.

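### A Shapiro-Wilk result decides whether change scores are compared as means, on an unnamed transformed scale or by ranks, so the secondary scales have no fixed effect estimate

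*SAP*

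**What the plan says.** SAP section 4.1 sets a general rule in three steps. First, "Shapiro-Wilktest will be used to test the normality". If normality fails, "the data will be presented as a median (interquartile range) and transformed to approximate a normal distribution". If no transformation is feasible, a "Wilcoxon test can be performed". The section gives no significance level for the normality test. It does not say whether the test is run in each arm, on pooled data or on residuals. It names no transformation and does not define when one is infeasible.

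Section 4.4.2 item 1 plans a comparison of means for cognition: "The mean value of changes in scores of global cognitive functions from baseline to 12 weeks will be compared using independent t-test". It then attaches the same gate, triggered by non-normality of any domain score: "if the transformation is not feasible, either the Wilcoxon test or Friedman M test will be used".

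Section 2.5.2 lists the questionnaire outcomes as changes, for example "Changes in subjects' self-efficacy scores from baseline to 12 weeks and 24 weeks" and "Changes in subjects' quality of life scores from baseline to 12 weeks and 24 weeks", with PHQ-9 and GAD-7 changes at the same two visits. None of the four items in 4.4.2 concerns these scales. For secondary analyses in general, 4.4.2 promises that "both 95% confidence intervals and p values will be reported".

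**The concern.** Every outcome affected is a change from baseline, so it takes negative and zero values. A logarithm, square root or Box-Cox transformation cannot be applied to such values without an added constant, and the SAP names neither a transformation nor a constant.

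The three branches answer different questions: a difference in means, a difference on some other scale, or a shift in ranks. Which one is reported would depend on a preliminary test that reacts to ties, rounding and tails, features that matter little to a comparison of means at this sample size. One scale could then carry a mean difference at week 12 and only a rank test at week 24, and two scales at the same visit could be reported in ways that cannot be compared. On the Wilcoxon branch the SAP does not say what the promised interval is an interval for.

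**Working it through.** **Size of the comparison.** Section 2.3 assumes response of 30% v 10%, two-sided alpha 0.05, 90% power and 20% loss. The two-proportion formula with unpooled variance gives n = (1.960 + 1.282)² × (0.3×0.7 + 0.1×0.9) / 0.2² = 78.8, so 79 per arm. Then 79 / 0.8 = 98.75, so 99 per arm and 198 in total. This reproduces the SAP. It has no bearing on the gate beyond setting the size: about 79 v 79 at week 12. At week 24, after the intervention arm is split 1:1, it is about 40 v 79.

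**What governs each scale.** Global cognition has a t-test with its own gate in 4.4.2 item 1. GSES, EQ-5D-3L, PHQ-9 and GAD-7 have no entry in 4.4.2, which leaves only 4.1.

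**How often the gate fires.** The SAP gives no distributions, so all of the following are assumptions. Scores were simulated with no arm difference, the Shapiro-Wilk test was taken at 0.05, and baseline-to-follow-up correlations were 0.5, 0.7 and 0.85, with 2,000 replicates per setting. The EQ-5D index used illustrative decrements.

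| Change score | Rejection in one arm of 79 |
|---|---|
| GAD-7 | 0.99–1.00 |
| EQ-5D index | 0.98–1.00 |
| PHQ-9, strong or moderate floor | 0.85–1.00 |
| PHQ-9, weak floor | 0.34–0.53 |
| GSES | 0.07–0.10 |
| BCAT, single domain | 0.51–1.00 |
| BCAT, mean of four domains | 0.09–0.35 |

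The simulated changes were almost symmetric (skewness within 0.02 of zero), so rejection comes from heavy tails, ties and rounding. The last two rows matter for 4.4.2 item 1, because its trigger refers to the domain scores while the outcome compared is the global score.

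A second model used overdispersed counts (gamma-Poisson pairs capped at 27, 80 per arm). With mean 4 and shape 1.2, about 39% of changes are negative and 22% zero, and the test rejects in at least one arm in 98% of trials. With mean 8 the figure falls to about 53% (shape 3) and 35% (shape 8).

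Rounding alone contributes less. Exactly normal changes recorded as integers are rejected in 18% (SD 3) or 13% (SD 4) of samples of 80, and in 56% or 20% of samples of 160. At SD 6 the rates are 7% and 9%.

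**Ambiguity when the arms disagree.** Under the mean-4 model the two arms give opposite Shapiro-Wilk results in about 25% of trials at 80 v 80 and about 48% at 40 v 80. The SAP does not say what follows.

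**Switching between visits.** If the rejection probability is p at each visit and the visits are treated as independent, the method differs between visits with probability 2p(1 − p). That is 2×0.5×0.5 = 50% at p = 0.5 and 2×0.3×0.7 = 42% at p = 0.3. Correlated visits would lower this.

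**Does the gate protect the error rate?** In the first set of simulations the ungated t-test had type I error 0.041–0.065 at 79 v 79 and 0.038–0.059 at 40 v 79. The Monte Carlo standard error is √(0.05×0.95/2000) = 0.005. In the count model the ungated t-test gave 4.5–6.0%, and the procedure that switches between t-test and Wilcoxon gave 4.6–6.1%. The transformation step was not simulated, because the SAP does not define one.

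**Gain from baseline adjustment.** In the mean-4 count model, ignoring the cap, the variance is 4 + 4²/1.2 = 17.33 and the covariance between visits is 13.33, so the correlation is 0.77. The variance of the adjusted comparison relative to the plain change comparison is (1 + 0.77)/2 = 0.885, about 12% lower.

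**The case against.** The best defence is that the gate does little damage. Type I error is near nominal with or without it, and against the t-test it costs only about 1–5 percentage points of power in the settings tried. The primary analysis is a chi-square test of proportions and is untouched. Section 4.1 sits among presentation rules, lists means and standard deviations among the descriptive statistics, and words the Wilcoxon step permissively. Its infeasibility clause could send signed changes straight to ranks, and a Hodges-Lehmann interval would keep the promise of a 95% interval.

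Much of this stands. A reader might infer that every questionnaire change will almost always fail the normality test. The documents give no distributions to support that, and under the assumptions above it is false for GSES and doubtful for PHQ-9 with a weak floor. A reader might also infer that mean differences disappear from the report or that false positives rise. Neither follows: means remain as descriptive statistics, and the error rate holds.

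What the defence does not answer is the choice of estimand. Permissive wording adds discretion. A Hodges-Lehmann estimate is a reasonable companion to the Wilcoxon test, but the SAP does not name it. Intermediate rejection rates are where a switch between visits is most likely. If 4.1 is only a presentation rule, the four questionnaires have no inferential rule at all.

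**Conclusion.** The point holds as a weakness in how the secondary analyses are fixed and should be corrected. The SAP lets a preliminary test choose among a mean, an unspecified transformed scale and ranks, for signed scores, possibly differently by scale and visit. How often it fires rests on assumed distributions: nearly always for GAD-7, EQ-5D and a PHQ-9 with a marked floor, about 35–55% of the time with a weaker floor, and seldom for GSES. The gate buys no measurable protection of type I error, and it does not inflate it either. The cost falls on interpretation: the between-arm mean difference is no longer the planned inference, and the 95% interval promised in 4.4.2 has no defined target. The primary endpoint is not affected.

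**What to change.** Delete the normality gate for efficacy change scores in both section 4.1 and section 4.4.2 item 1, including the open choice between the Wilcoxon and Friedman tests. Replace it with one rule covering the global cognitive score, GSES, EQ-5D-3L, PHQ-9 and GAD-7:

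- **Analysis:** compare groups on the original scale whatever the Shapiro-Wilk result, by a linear model of the follow-up score on randomised group and baseline score with robust standard errors. Report the mean difference with its 95% interval and p value.
- **Groups:** intervention v control at week 12; continue-training v control and stop-training v control at week 24.
- **Sensitivity:** one pre-stated Wilcoxon test on the changes with a Hodges-Lehmann estimate and interval.
- **Description:** keep median (IQR) for description only.

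Keeping the plain t-test that 4.4.2 already names, ungated, would also cure the defect. The baseline-adjusted model is preferred for its precision. The cost is SAP wording and a few lines of code. The small downside is that a skewed scale is summarised by a mean difference, which the rank analysis covers.

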#### ***4.2 Timing of analysis***

The data clearance and analysis will be initiated after all 200 participants finished their 24-week visiting.

#### ***4.3 Discontinuing/Intervention Deviation***

Given the intervention's nature, the study will not result in any foreseeable harm or an objective need to stop the intervention. The patient will be informed that he or she may request a suspension of training or withdrawal from the study at any time for any reason and

that this will not affect his or her routine medical treatment. If the withdraw occurs, the existing data will be retained and the subsequent data will be marked as missing data. This study defines missing follow-up as an uncertain primary outcome in randomized participants. If a participant fails to return to the clinic for a scheduled study visit, the site must make every effort to reconnect with the participants in certain window. In general, retrospective visits are not permitted. However, the adverse measure will still be recorded and involved.

There are no plans to modify the assigned intervention. If adverse events occur, investigators will determine whether continued intervention is harmful to the safety or health of the participants, or sponsor requires participants to permanently stop the intervention, then the patient's intervention will be discontinued.

#### ***4.4 Efficacy analysis***

##### ***4.4.1 Primary efficacy analyses***

The null hypothesis  $H_0$  for the primary outcome will be there is no difference between the proportion of patient demonstrated global cognitive function improvement in the cognitive training (intervention) group and the positive control group. The alternative hypothesis  $H_1$  will be the proportion in cognitive training group is different to the positive control group.

$$H_0: \mu_x = \mu_a$$

$$H_1: \mu_x \neq \mu_a$$

Where  $\mu_x$  and  $\mu_a$  represented the proportion of patients with BCAT score changes greater than  $0.67SD$  from baseline to 12 weeks in the intervention and the control group, respectively.

The proportion of subject with global cognitive function improvement in the intervention group will be compared to the proportion in the control group using Pearson chi-square test.

The improvement in global cognitive function is defined as a 0.67SD increase in the overall BCAT test scores after 12 weeks training, when compared to the baseline scores. The estimated difference in proportion will be examined by using 95% confidence intervals for point estimations of endpoint occurrence probability. The proportion of subjects demonstrating improvement will be also analyzed for each subgroup, responding.

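### The primary responder rule in SAP Section 4.4.1 requires a change above 0.67 SD, so a gain of exactly 2 points, which Section 2.5.1 equates with clinically significant improvement, does not count

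*SAP*

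**What the plan says.** Section 4.4.1 gives the primary responder rule twice. Under the hypotheses, the two parameters "represented the proportion of patients with BCAT score changes greater than" 0.67 SD between baseline and week 12, which is a strict inequality. A little further on, "The improvement in global cognitive function is defined as a 0.67SD increase in the overall BCAT test scores after 12 weeks training", which is most naturally read as at least that much.

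Section 2.5.1 gives the same threshold with a points equivalent: clinically significant improvement is an overall Z-value "0.67 SD (2 points of task score) higher than the baseline Z-value". It forms the global measure by averaging: "The global cognitive function score will be calculated as the average of scores across each cognitive domain". It then refers to a look-up table for the Z scale: "The Z-value for each cognitive domain can be obtained by referring to the Z score conversion table". Table 1 lists scores 1 to 19 against Z from -3.00 to 3.00, to two decimals.

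The 24-week secondary outcome in Section 2.5.2 is stated with the points figure only: "The proportion of clinically significant improvement (2 points of task score) in global cognitive function from baseline at 24 weeks". Section 2.1 gives the 12-week primary outcome as 0.67 SD above baseline, with no points figure and no inequality.

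None of these sections says whether a gain of exactly 2 points is a response, or whether Z is rounded before the comparison.

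**The concern.** The threshold decides who counts as a responder in the sole primary endpoint, a yes/no outcome compared by Pearson chi-square. A program needs an inequality, a number and a scale. The SAP supports at least three rules: above 0.67 SD, at least 0.67 SD, and at least 2 points. They coincide only if 2 points is treated as exactly 0.67 and ties count. By the SAP's own table 2 points is not above 0.67, so the rule attached to the hypotheses excludes the gain that Section 2.5.1 uses to define clinical significance.

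Two analysts following the same text could report different primary responder counts from the same data. Section 4.2 starts data cleaning and analysis after the last 24-week visit, so if the wording stays as it is, the choice falls to be made with the data in hand.

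**Working it through.** **1. The plan's sample size (Section 2.3 and the dropout table).** Inputs: 30% and 10%, two-sided alpha 0.05, power 90%, 20% loss. With unpooled variances:

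n = (0.3×0.7 + 0.1×0.9) × (1.960 + 1.282)² / 0.20² = 78.8, so 79 per arm.

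79 / 0.80 = 98.75, so 99 per arm and 198 in total. This reproduces the plan. Exact power of the Pearson test at 79 per arm is 0.902.

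**2. Points to SD (Table 1).** Spacing = (3.00 − (−3.00)) / (19 − 1) = 0.3333 SD per point. Two points = 0.6667 SD. That figure follows from the spacing; it is not printed in the table.

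**3. Two-point gains from the printed Z values.** A gain of 2 is possible from 17 starting scores (1 to 17).

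| Starting score | Printed Z difference |
|---|---|
| 3, 6, 9, 12, 15 (5 scores) | 0.66 |
| the other 12 | 0.67 |
| any | never above 0.67 |

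**4. Four-domain means with a mean gain of exactly 2.0 points.**

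- 8, 8, 8, 8 to 10, 10, 10, 10: mean Z change 0.67. Fails above 0.67, passes at least 0.67.
- 8, 8, 8, 9 to 10, 10, 10, 11: (3×0.67 + 0.66) / 4 = 0.6675. Fails both unless rounded.
- 9, 9, 9, 9 to 11, 11, 11, 11: 0.66. Fails both, rounded or not.
- 8, 8, 8, 8 to 9, 9, 10, 12: (0.34 + 0.34 + 0.67 + 1.34) / 4 = 0.6725. Passes both, purely through rounding in the table.

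When all four domains rise by 2, tabulated Z never exceeds 0.67. Uneven gains averaging 2.0 can do so, as in the last line, but rarely: about 0.3–0.4% of such patients in simulation, against about 12–13% who reach at least 0.67. On unrounded Z, 2/3 fails both rules every time. Changing the inequality alone is therefore not a repair.

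**5. Can a patient land on the boundary?** If domain scores are integers, as Table 1 prints them, a four-domain mean moves in steps of 0.25 and exactly 2.0 is attainable. The SAP does not state the score format beyond the table.

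**6. Illustration of size (assumptions not in the SAP).** Assume integer domain changes, an SD of global change of about 1 to 2 points, and 30%/10% referring to the inclusive 2-point rule. Moving from inclusive to strict shifts the cut by one 0.25-point step, so the strict rate is approximately 1 − Φ(z + 0.25/SD), where z is the normal quantile of the inclusive rate. For SD 1.00: 1 − Φ(0.524 + 0.25) = 21.9%, and 1 − Φ(1.282 + 0.25) = 6.3%. Simulation gives:

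| SD of global change | Exactly 2.0 (active / control) | Strict rates | Power, 79 per arm | Power, 89 per arm |
|---|---|---|---|---|
| 1.00 | 8.1% / 3.7% | 21.9% / 6.3% | 0.838 | 0.874 |
| 1.39 | 6.0% / 2.8% | 24.0% / 7.2% | 0.859 | 0.891 |
| 1.98 | 4.3% / 2.0% | 25.8% / 8.0% | 0.874 | 0.904 |

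The 89 comes from the 224 enrolled in Section 4.9, assuming equal arms and 20% loss: 112 × 0.80 = 89.6. At 30%/10%, power there is 0.929.

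**The case against.** The strongest reply is that this is rounding. To two decimals 2/3 is 0.67, Section 2.5.1 gives the meaning in points, and Section 2.5.2 uses points alone, so the intent is almost certainly a 2-point gain. As a reading of intent this stands, and the fix writes it down. It does not rescue the text: 0.67 is still not greater than 0.67, the SAP gives no rounding rule, and gains starting from 9 in every domain come to 0.66 even at two decimals.

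It is also fair that the SAP contains no wrong calculation here. This is a defect of endpoint definition, and the sample size stands.

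Stronger readings are tempting, but the document does not support them:

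- *The trial is underpowered.* The loss in the illustration needs an assumed SD of change and needs 30%/10% to refer to the inclusive rule. Section 2.3 attributes its assumptions to previous studies and names no inequality. If those rates already refer to the strict rule, nothing is lost. At the 224 enrolled the illustrated power is close to the 90% target.
- *The result is biased or the type I error inflated.* Any single rule applies alike to both arms.
- *The score scale and the Z scale classify patients materially differently.* Table 1 prints a range of Z around each score, so with a continuous Z a 2-point domain gain could lie anywhere from 0.33 to 1.00 SD. Section 2.5.1, however, describes Z as looked up from the score. Under that look-up the two scales agree apart from the table's rounding.

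**Conclusion.** The endpoint definition is wrong as written. The rule attached to the primary hypotheses is strict at 0.67 SD, while the SAP's own equivalent for that threshold, 2 points, is 2/3 SD by Table 1's spacing and 0.66 or 0.67 by its printed values. A patient who gains exactly 2 points is therefore a non-responder under the literal hypothesis, apart from rare uneven gains that table rounding lifts over the line. A cut-off of at least 0.67 fails all such gains on unrounded Z and many of them on tabulated Z.

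The contradiction rests only on the SAP's text and table. That it can affect a patient rests on domain scores being integers. The share of patients affected cannot be obtained from the SAP. The 4–8% of active and 2–4% of control patients at the boundary, and power of roughly 84–87% at 79 per arm or 87–90% at about 89, are illustrations under the stated assumptions. It should be fixed before analysis, because it leaves the primary responder count open.

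**What to change.** Before analysis, in Section 4.4.1 replace the strict 0.67 SD wording under the hypotheses with at least 2 points (2/3 SD). Use one inclusive rule in Sections 2.1, 2.5.1, 2.5.2 and 4.4.1:

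> A patient is a responder if the unrounded mean of the four domain BCAT scores has risen from baseline by 2.0 points or more (equivalently 2/3 SD). Responders are not classified from the two-decimal Z values in Table 1.

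Section 2.3 should say which rule its 30% and 10% refer to only if the sponsor can confirm this from the source study; otherwise it should make no such statement.

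The cost is SAP wording only. Sample size and data collection do not change.
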